8. STORAGE OF DATA AND SAMPLES

We will follow NIH guidelines to prevent identification of study participants and other violations of subject confidentiality. Information will be stored using a confidential case number, and no identifiers (name, address, phone number, etc.) will be used that could allow direct linking of database information to individual subjects. Secure e-mail will be used for all electronic communications of subject information between investigators. Blood samples will be discarded at the end of the study. Demographic and clinical data will be archived on a password-protected server.

All data will be stored on the NIMH server under password protected accounts accessible only to the principal investigator and directly involved study personnel to preserve subject privacy. All data is regularly backed up, either by the NIMH system administrator, or by NIMH CIT personnel.

9. RISKS/DISCOMFORTS

Potential risks from this study include those associated with: a) medical examinations including phlebotomy for blood and urine analysis, b) radiation exposure from the PET and transmission scans, c) Pharmacological effects, d) PET scanning, e) placement of arterial, f) placement of venous lines, g) blood sampling, h) MRI, i) ECG.

9A. Medical examination and laboratory testing

Medical examinations, including phlebotomy for blood analysis are not associated with more than minimal risks. There is usually some discomfort when the needle is inserted for phlebotomy.

9B. Radiation exposure risks

Radiation exposure in this protocol will be from [11 C]ER176 and the associated transmission scans. The radiation exposure from [11 C]ER176 is unknown, but [11 C]-labeled compound generally show very similar dosimetric values of about 5 μ Sv/MBq (Zanotti-Fregonara and Innis 2012) or about 0.38 rem for a 20 mCi injection. We wish to maintain flexibility in the choice of PET cameras, which differ in the dose from the transmission scan. Among the various PET cameras, the PET/CT has the highest dose from the transmission scan. The effective doses for one head, one chest and one whole-body transmission scans from a PET camera that uses a 68 Ge transmission source are 0.01, 0.01, and 0.05 rem respectively. The effective doses for one head, one chest and one whole-body transmission scans from a PET/CT camera that uses CT transmission source are 0.06, 0.21, and 0.66 rem respectively. In addition, we routinely include the dose from two transmission scans in the event that it must be repeated in a subject. The total effective dose including emission and transmission scans for any individual subject in Phase 1 is about 0.92 rem and in Phase 0 or Phase 2 is about 1.7 rem – which are well below the NIH RSC guideline of 5 rem.

All subjects will be asked about any prior research participation involving radiation exposure so that the total exposure, in combination with the present study, does not exceed an effective dose of 5 rem per 12 months.

9C. Pharmacological effects

We inject PET radioligands at such low mass doses at the tracer level (typically less than $10~\mu g$) that no pharmacological effects are expected. To ensure safety, new ligands are first tested in animals (e.g. rodents) typically at 100X the human equivalent dose (HED). Ligands are considered safe for administration in humans if the no observed adverse effect level (NOAEL) is at least 100X HED. We performed an acute toxicity study in male and female rats at 100X HED considering a maximal human dose of $10~\mu g$ per subject. However, in this study, slight ataxia was observed immediately after intravenous administration in $10~\sigma f$ 10 males and 6 of 10 females in the ER176 treated group. The ataxia was transient and noted within a few minutes after injection. The animals were not examined again until about two hours after injection, at which time the ataxia was gone.

To better understand this adverse effect, we commissioned another study using lower doses and observation at more frequent time points. Three groups of 10 male and 10 female

rats were intravenously administered ER176 at 100X, 50X, and 25X HED. On this repeat study, none of the animals at 100X HED and only one of the animals at 50X HED showed ataxia. Please note that we used the same batch and formulation of the test compound. Thus, this behavioral finding was not robust enough to be reproducible at the 100X HED dose, and may depend on the somewhat variable condition of the test animals. Nevertheless, because one of the 20 animals at 50X HED showed ataxia, the NOAEL for ER176 was 25X HED.

In view of these results in rats, we propose the following safety measures for using [\$^{11}C]ER176 in humans.

- (a) Decrease the maximal mass dose: For all of our other INDs for radiopharmaceuticals, the maximal mass dose is 10 μ g, whereas for ER176, we will limit the maximal mass dose to 5 μ g.
- (b) Decrease the infusion rate: Because the ataxia in rats was transient and ended within a few minutes of its bolus injection, it was likely related to transient high plasma concentrations of ER176. To decrease the plasma concentration in human subjects, we will infuse [11C]ER176 over three minutes, rather than the 0.5 to 1.0 minute commonly used in PET studies. Thus, the combination of injecting half the maximal dose over a three-timeslonger time period would be expected to decrease the peak plasma concentrations by about six-fold.

In case of tracer extravasation, we will stop the study, remove the venous line from the arm, and apply cold to the site.

9G. Blood sampling

Participants will have arterial and venous blood sampling of about 250 mL during the entire course of the study. The amount of blood drawn will not exceed 400 mL. Some of the blood will be collected via phlebotomy and some through venous and arterial line. Blood sampling may lead to the formation of a small subcutaneous hematoma caused by blood leaking from a punctured blood vessel. This hematoma causes only minor discomfort. It is not dangerous and requires no treatment other than reassuring the patient. There is also a small risk of infection at the site of the needle puncture, which can be readily treated with antibiotic therapy. We will ask participants not to donate blood for a period of eight weeks after participation in this study.

9H. MRI

People are at risk for injury from the MRI magnet if they have pacemakers or other implanted electrical devices, brain stimulators, some types of dental implants, aneurysm clips (metal clips on the wall of a large artery), metallic prostheses (including metal pins and rods, heart valves, and cochlear implants), permanent eyeliner, implanted delivery pump, or shrapnel fragments. Welders and metal workers are also at risk for injury because of possible small metal fragments in the eye of which they may be unaware. Subjects will be screened for these conditions before having any scan, and if they have any, they will not receive an MRI scan.

It is not known if MRI is completely safe for a developing fetus. Therefore, all women of childbearing potential will have a pregnancy test performed no more than 24 hours before each MRI scan. The scan will not be done if the pregnancy test is positive. People with fear of confined spaces may become anxious during an MRI. Those with back problems may have back pain or discomfort from lying in the scanner. The noise from the scanner is loud enough to damage hearing, especially in people who already have hearing loss. Everyone having a research MRI scan will be fitted with hearing protection. Subjects will be asked to complete an MRI screening form for each MRI scan you have. There are no known long-term risks of MRI scans.

9I. ECG

There is no risk associated with having an ECG. The patient may feel uncomfortable while the electrodes are attached to the chest. The conductive gel sometimes causes some mild irritation.

10. SUBJECT SAFETY MONITORING

Participants will be carefully monitored by clinical staff throughout the study. Participants will be asked about the presence of adverse events throughout the procedure and also for at least an hour following the PET procedure. In view of the transient ataxia observed in acute toxicity studies in rats at 50X HED, and as those effects occur at first few minutes of the study, we will ask the participants to be particularly vigilant of any subjective effects during the early portion of the study. At the end of the study, we will ask the person to gradually stand up. We will be there to assist as needed and ask if they have any difficulty standing or walking. We will release subject only after we and they feel entirely normal and are walking normally. Participants will be monitored during the PET procedure. The site of the catheter insertion will be carefully monitored for signs of bleeding.

10A. Parameters to be monitored

Pulse rate, temperature, blood pressure, respiratory rate, and ECG will be recorded within 3 hours before tracer injection for all the subjects of the study, and again at about 15, 30, 90 and 120 minutes (end of the scan) after tracer injection. Monitoring will be performed by the credentialed clinician. Laboratory tests (CBC, chemistry panel, thyroid panel, urine analysis, pregnancy test) will be performed ~3 hrs before the tracer injection and will be repeated (excluding pregnancy test) ~24 hours after tracer injection. If the subject will not be available at the above-mentioned times, blood and urine samples will be taken shortly after the PET procedure.

Follow-up phone calls to participants will be made at 24 hours post-injection.

All adverse events (AEs) will be recorded on the case report form (appended to the present protocol). All AEs, including clinically significant abnormal findings on laboratory evaluations, regardless of severity, will be evaluated until satisfactory resolution.

10B. Criteria for individual subject withdrawal

Subjects will be removed from the study if they become pregnant, are unable to continue to cooperate, or have an alteration in clinical status needing medical intervention. Subjects may withdraw from the trial at any time at their own request. The Investigators may withdraw a subject for safety or behavioral reasons.

11. OUTCOME MEASURES

Primary outcome measures:

- 1. [¹¹C]ER176 binding, with regards to identifiability and stability over time of distribution volume calculated with compartmental modeling.
- 2. Biodistribution and dosimetry of [¹¹C]ER176.

Secondary outcome measures:

1. The effect of polymorphisms of TSPO that may explain the differences in [11C]ER176 binding. TSPOs are present in both brain and lung, and the SNP affects

binding in both organs. Compared to brain, lungs have much higher density of TSPO and may be more effective in assessing whether ER176 is sensitive to the SNP.

12. STATISTICAL ANALYSIS

Brain imaging data will be analyzed with compartmental modeling using a nonlinear least squares analysis, graphical analysis of integration plot, and multilinear regression analyses. PET and MRI scans will be coregistered for anatomic definition of regions of interest. Percent SUV will be calculated in various brain regions. Parametric images will be created using PMOD software (PMOD Technologies Ltd., Zurich, Switzerland). The kinetic modeling will give us the [11 C]ER176 binding values, and their identifiability and stability over time. Because of inter-subject variability in pharmacokinetics and metabolism of PET radioligands, sample sizes of approximately 15 per group are required in such studies (Fujita *et al* 1999; Ichise *et al* 2003; Koeppe *et al* 1999).

In order to evaluate genotype sensitivity of [11 C]ER176 in brain we calculated the percent difference in binding values necessary to differentiate between HABs, MABs and LABs. This was based on our previous results with [11 C]PBR28 brain scans in healthy volunteers of different genotypes (Kreisl *et al* 2012). The mean V_T of HH subjects (HABs; n = 9) for whole brain was 4.5 mL/cm³ with a standard deviation of 1.4 mL/cm³. In addition, the V_T of HH subjects was 40% higher than the V_T of HL subjects. Assuming similar SD/Mean for [11 C]PBR28 and [11 C]ER176, we can calculate how much of a difference in mean V_T can be detected between genotypes. Power analysis based on V_T of HH subjects from [11 C]PBR28 scans showed that with a sample size of 10 for each binder group, a power of 80% and alpha of 0.05 the percent difference to be detected from the mean value of a HAB is 40%. That is, the difference in mean V_T between HH and other genotypes should be >40% for it to reach a statistical significance with a sample size of 10. Therefore, we require a recruitment of 12 subjects for each group (36 in total for HABs, MABs and LABs) under Phase 1 considering some withdrawals.

Similar to brain, we calculated the percent difference in lung uptake (measured as area under time-activity curve) necessary to differentiate between HABs, MABs and LABs based on our previous results with [11 C]PK 11195 in healthy volunteers (Kreisl *et al* 2010). The mean lung uptake for [11 C]PK 11195 in HABs (n = 5) was 25.6 SUV • min with a standard deviation of 3.7 SUV • min. In addition, lung uptake was significantly higher (by 27%) in HABs than in LABs. Assuming similar SD/Mean for [11 C]PK 11195 and [11 C]ER176, we can calculate how much of a difference in mean lung uptake can be detected between genotypes. Power analysis based on [11 C]PK 11195 lung uptake in HABs showed that with a sample size of six for each binder group, a power of 80%, and alpha of 0.05, the percent difference to be detected from the mean value of an HAB is 23%. That is, the difference in mean lung uptake between HH and other genotypes should be >23% for it to reach statistical significance with a sample size of six.

In whole body imaging studies, organ time-activity curves will be obtained from the dynamic PET images, and used to calculate organ residence times. Residence time of the urinary bladder may be calculated using a dynamic bladder model (Cloutier *et al* 1973). The residence times will be used in OLINDA/EXM (http://www.doseinfo-radar.com/OLINDA.html) to obtain radiation-absorbed dose estimates. To take into account inter-subject variability, radiation absorbed doses are usually estimated from approximately 6-8 subjects (Fujita *et al* 2002; Seibyl *et al* 1994; van Dyck *et al* 1996). To also take into account possible gender differences, we propose to study approximately an equal number of

male and female subjects in the whole body imaging study. Currently we do not plan to match the genotype for subject recruitment under Phase 2 dosimetry scans but if we do find any unexpected differences between different binders from Phase 1 study, we will do at least 3 subjects for each binder group (9 subjects in total). Considering the requirement of one subject for the initial Phase 0 and any possible withdrawals, we seek a total of 11 subjects for Phase 2.

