2. PRECIS

i. Objective

Translocator protein 18 kDa (TSPO) is highly expressed in activated microglia and reactive astrocytes in brain, and it may, thereby, be a useful biomarker of neuroinflammation. We developed [\$^{11}\$C]PBR28 as a positron emission tomographic (PET) radioligand to bind to TSPO and measure its density. Although [\$^{11}\$C]PBR28 has high in vivo specific signal, it is very sensitive to the high and low affinity states of TSPO, which are caused by a single nucleotide polymorphism (SNP) in the fourth exon of the TSPO gene. This co-dominant mutation yields three genetic groups: HH, HL, and LL, where H is the high-affinity form and L is the low affinity form. The frequency of the L allele is ~30%; thus, the frequency of the LL homozygote is ~9%. The affinity of PBR28 to H and L forms differs about 50 fold; thus, LL carriers provide no measureable signal in brain from [\$^{11}\$C]PBR28. We recently developed a new TSPO ligand ER176, the affinity of which differs by only 1.2 fold and therefore LL carriers should provide measureable brain uptake. The purpose of this study is to assess the potential of [\$^{11}\$C]ER176 to image TSPO in brain, characterize its binding sensitivity in lung of healthy subjects from all three genetic groups, and to do whole-body imaging for biodistribution and estimation of radiation dosimetry in humans.

The present protocol will use a new PET ligand—[¹¹C]ER176 —to 1) perform an initial whole-body scan after [¹¹C]ER176 injection in a single healthy volunteer to confirm wide-spread distribution of radioactivity to different body organs (Phase 0); 2) perform kinetic brain scans in healthy volunteers of 3 different genotypes, with about half of these volunteers undergoing lung scans in the same session (Phase 1), and; 3) perform whole-body imaging in healthy volunteers (Phase 2).

This study will assess the relative robustness of absolute quantitation of TSPO in the brain of healthy subjects, using an arterial input function and pharmacokinetic modeling. In addition, lung imaging will provide in vivo binding sensitivity of [\frac{11}{C}]ER176 to TSPO genotype. Furthermore, the whole-body imaging would estimate the radiation-absorbed doses for future use of [\frac{11}{C}]ER176 in clinical studies.

ii. Study Population

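### The brain sample-size paragraph sets two 40% figures on different bases side by side; the PBR28 HH-HL difference is 28.6% of the HAB mean, for which 10 per group gives about 50-65% power

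*Protocol*

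**What the plan says.** Section 12 takes its planning values from earlier [11C]PBR28 scans in healthy volunteers: an HH mean V_T of 4.5 mL/cm³ from nine subjects, and an SD of 1.4 mL/cm³. It adds that "the V_T of HH subjects was 40% higher than the V_T of HL subjects".

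Under the assumption introduced by "Assuming similar SD/Mean for [11 C]PBR28 and [11 C]ER176", it reports a power calculation for 10 subjects per genotype at 80% power and 5% alpha. The result is given in these words: "the percent difference to be detected from the mean value of a HAB is 40" per cent. The next sentence explains this as meaning that HH must differ from the other genotypes by more than 40% for the result to be statistically significant. From this the section concludes that "we require a recruitment of 12 subjects for each group", with the extra two covering withdrawals.

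The brain genotype comparison is described under the primary outcome measures in the Precis (iv. Outcome Measures). Section 11 lists the effect of the polymorphism as secondary.

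**The concern.** Two figures of 40% stand a few lines apart, and the text does not say that they have different denominators. One is an observed effect relative to the HL mean. The other is a detectable effect relative to the HAB (HH) mean. They look matched, so the paragraph can be taken to show that the design detects an effect the size of the one seen with PBR28.

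This matters because the study's expectation, from in vitro data, is that ER176 is not sensitive to genotype. A non-significant HH-HL comparison is the hoped-for result, and low power makes it more likely. The reader needs to know how much such a result could show.

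**Working it through.** **Inputs, all from Section 12:** HH mean V_T 4.5; SD 1.4 (the only SD given), so SD/mean = 1.4/4.5 = 31.1%; HH 40% above HL; n = 10 per group; power 80%; alpha 0.05. Sidedness is not stated. I assume two-sided, because one-sided gives a detectable difference of 34.6% (normal) or 36.0% (t) and does not return 40%.

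**1. Reproducing the plan's figure.** Standard error of a difference in means: 1.4 × √(2/10) = 0.626.
- Normal approximation: (1.960 + 0.842) × 0.626 = 1.754 mL/cm³; 1.754/4.5 = 39.0%.
- Noncentral t, 18 df: 1.855 mL/cm³; 1.855/4.5 = 41.2%.
- For exactly 40% (0.40 × 4.5 = 1.80 mL/cm³), power is 82.0% (normal) or 77.6% (t).

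The stated 40% is right to rounding. It uses only the HH mean, the SD and n; the HH/HL ratio does not enter.

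**2. The PBR28 difference on the HAB base.** HL mean = 4.5/1.4 = 3.21. Difference = 4.5 − 3.21 = 1.29 mL/cm³. 1.286/4.5 = 28.6%. This is below both 39.0% and 41.2%.

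**3. Power for 1.29 mL/cm³, two-sided 0.05.** With common SD 1.4 and n = 10 the noncentrality is 1.286/0.626 = 2.05, against a t critical value of 2.10.

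| Assumption | n = 10 | n = 12 |
|---|---|---|
| t-test, SD 1.4 in both groups | 49% | 58% |
| Normal approximation, SD 1.4 | 54% | 61% |
| t-test, constant SD/mean (HL SD 1.0, pooled SD √((1.96 + 1.00)/2) = 1.217) | 61% | 70% |
| t-test on log scale (difference ln 1.4 = 0.336, SD √ln(1 + 0.311²) = 0.304) | 65% | 74% |

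None reaches 80%, even if all 12 recruits per group are evaluable. For 80% by t-test, about 20 per group would be needed with SD 1.4, or 16 with constant SD/mean.

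**4. HH against LL.** The protocol gives no PBR28 V_T for LL. If each L allele lowers V_T by the same 1.29 mL/cm³ (an assumption), the HH-LL difference is 2 × 1.286 = 2.57 mL/cm³, or 57% of the HH mean. The noncentrality is 2.571/0.626 = 4.11, and the pairwise t-test at n = 10 has about 97% power.

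**5. The significance threshold.** At n = 10 and SD 1.4 an observed difference is significant once it exceeds 2.101 × 0.626 = 1.315 mL/cm³, and 1.315/4.5 = 29.2% of the HH mean. The 40% figure is the true difference detected with 80% power, which is a different quantity.

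**The case against.** A reader might infer that the plan computed its sample size by mistaking one 40% for the other, or that it claims 80% power for the PBR28 HH-HL difference and really has 49%. The document supports neither reading. It names the HAB mean as the base of the detectable difference, that figure reproduces, and the ratio plays no part in it. Nowhere does it say that n was chosen to detect the PBR28 HH-HL effect. The 49% is also the low end of a range; the normal formula, which returns the plan's n = 10 for a 40% difference, gives 54%.

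It can also be said that the plan compares HH with the other genotypes, LL included, so strong sensitivity of the PBR28 kind would probably show up in HH-LL. That stands, given roughly additive steps. It limits the weakness to the HH-HL pair.

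A slope of V_T on the number of L alleles might seem to rescue the power. With equal groups the slope estimate is half the HH-LL difference, so it adds almost nothing to the existing pairwise test and does not strengthen HH-HL. It also requires equal steps, whereas the Precis says only "This co-dominant mutation yields three genetic groups: HH, HL, and LL", which does not imply equal steps in V_T.

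What remains is that the PBR28 effect is quoted beside the detectable difference on another base, with no conversion, and is smaller than the design can reliably detect.

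**Conclusion.** The point holds as a fault in the sample-size justification. The plan's 80% power for 40% of the HAB mean is correct to rounding. The PBR28 HH-HL difference quoted beside it is 28.6% on that base, and power for it with 10 evaluable per group is about 50-65%, depending on the variance assumption and the method. These figures rest on a two-sided 5% test, no multiplicity adjustment, and the protocol's own assumption that SD/mean carries over from PBR28 to ER176.

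A non-significant HH-HL result would therefore leave PBR28-like sensitivity between those two groups open. HH-LL is well powered if the steps are additive. Separately, the sentence that treats 40% as the threshold for significance is wrong: about 29% observed is enough at n = 10.

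**What to change.** In Section 12, put both figures on the HAB-mean base and state that:
- the PBR28 HH-HL difference is 1.29 mL/cm³, or 28.6% of the HAB mean, below the roughly 40% detectable with 80% power at 10 evaluable per group;
- power for a difference of that size is about 50-65%, with the assumptions named;
- a non-significant HH-HL comparison will not be read as absence of genotype sensitivity.

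Replace the sentence on the 40% requirement for significance with one saying that a true difference of about 40% of the HAB mean is detected with 80% power, while an observed difference of about 29% already reaches significance under the planning SD.

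The cost is a few sentences and a less favourable statement of what the HH-HL comparison can show. No subjects, scans or change of test are required.

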We will select up to 36 healthy adult female and male volunteers (age 18 and older) of 3 different TSPO genotypes for brain imaging, and up to 11 additional healthy volunteers for whole body dosimetry analysis.

iii. Design

For absolute quantification of TSPO, up to 36 healthy controls (up to 12 each of three TSPO genotypes) will have brain PET imaging using [\$^{11}\$C]ER176 and these subjects will have the arterial line and a brain MRI scan. In about half of those subjects from each genotype group, lungs will be scanned in the same session. For radiation dosimetry of [\$^{11}\$C]ER176, up to 11 subjects will have whole-body PET imaging. These subjects will not have arterial line and MRI scans.

iv. Outcome Measures

The primary outcome measures are: (a) To assess absolute quantitation of TSPO with [\frac{11}{C}]ER176, we will determine the identifiability and time stability of distribution volume in the brain calculated with compartmental modeling. The difference in mean distribution

volumes among subjects with different genotypes would be used to evaluate the genotype sensitivity of [¹¹C]ER176. (b) To assess whole-body biodistribution and dosimetry of [¹¹C]ER176 we will use the organ time-activity curves.

As secondary outcome measure, we will examine the effect of polymorphism on [\frac{11}{C}]ER176 binding in lungs because lungs have much higher density of TSPO and may be more effective to show whether ER176 is sensitive to the SNP.

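### The genotype detectable differences (40% brain, 23% lung) are for one comparison at alpha 0.05, though three genotypes are compared; the lung figure falls short of 80% power even for one two-sided t-test

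*Protocol*

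**What the plan says.** The Precis describes three genotype groups ("This co-dominant mutation yields three genetic groups: HH, HL, and LL") and, under the primary outcome measures, says that the difference in mean distribution "volumes among subjects with different genotypes would be used to evaluate the genotype sensitivity" of the tracer. It lists the lung comparison as secondary. Section 11 lists the polymorphism effect in both organs as secondary.

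In Section 12 the aim of the brain calculation is three-way: "we calculated the percent difference in binding values necessary to differentiate between HABs, MABs and LABs". The calculation uses an HH mean V_T of 4.5 mL/cm³ and SD of 1.4 from an earlier tracer, and concludes that "with a sample size of 10 for each binder group, a power of 80% and alpha of 0.05 the percent difference to be detected" is 40% of the HH mean. That 40% is then applied to HH against the other genotypes, and recruitment of 12 per group (36 in all) is derived from it. The lung paragraph repeats the argument with mean 25.6 and SD 3.7 SUV·min, six per group, and a detectable difference of 23%.

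Section 12 names no test, no sidedness and no order of comparisons. It does not say whether 0.05 applies to each comparison or to all of them together. Its dosimetry paragraph also makes a recruitment decision depend on the genotype result: "if we do find any unexpected differences between different binders from Phase 1 study, we will do at least 3 subjects for each binder group".

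**The concern.** A detectable difference computed for one comparison is offered as the basis for a question with at least two contrasts per organ (HH–HL and HH–LL), or three if HL–LL counts. Nothing in the calculation allows for the second or third.

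Insensitivity to genotype is the property ER176 was developed for. If each contrast is tested at 0.05, an insensitive tracer has more than a 5% chance of appearing sensitive in an organ. If the error rate is instead shared among the contrasts, the printed 40% and 23% are too small and a real difference is more likely to be missed. Since insensitivity is the expected result, a missed difference is the costlier error. Lung was added because it should show sensitivity best, and lung has the larger shortfall.

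**Working it through.** **Inputs (Section 12).** Brain: mean 4.5, SD 1.4, n = 10 per group, difference 0.40 × 4.5 = 1.80. Lung: mean 25.6, SD 3.7, n = 6 per group, difference 0.23 × 25.6 = 5.89. Power 80%, alpha 0.05. Assumed: two-sided tests and the HH SD in every group.

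**Step 1: the printed figures.** For one comparison of two means by the normal approximation, the detectable difference is (1.960 + 0.842) × SD × √(2/n).
- Brain: 2.802 × 1.4 × √(2/10) = 1.754, or 39.0% of 4.5. Printed: 40%.
- Lung: 2.802 × 3.7 × √(2/6) = 5.985, or 23.4% of 25.6. Printed: 23%.

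The t-based versions use the noncentral t distribution, with df = 2n − 2 for two groups or 3n − 3 if the SD is pooled over three.

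| Two-sided, one comparison, 80% power | Brain, n = 10 | Lung, n = 6 |
|---|---|---|
| Normal approximation | 39.0% | 23.4% |
| Two-group t | 41.2% | 26.0% |
| SD pooled over three groups | 40.4% | 25.0% |

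The printed brain figure lies within this range. The printed lung figure is matched only by the normal approximation, which is optimistic with six per group. A one-sided t-test would give 22.3% in lung, but the same choice gives 36.0% in brain, so it does not account for both printed figures.

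**Step 2: power for one comparison at the printed difference.** The noncentrality is difference ÷ (SD × √(2/n)).
- Brain: 1.80 ÷ 0.626 = 2.875. Power is 82% (normal), 78% (t, 18 df), 79% (pooled, 27 df).
- Lung: 5.89 ÷ 2.136 = 2.756. Power is 79% (normal), 70% (t, 10 df), 73% (pooled, 15 df).

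**Step 3: false positives with unadjusted tests.** In simulation with all genotypes equal and two-sided t-tests at 0.05, the chance of at least one significant difference per organ is about 9% for the two HH contrasts and about 12% for all three pairs, in brain and in lung.

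**Step 4: 5% held within each organ by Bonferroni.** The alpha per test is 0.05/2 = 0.025 or 0.05/3 = 0.0167. Ranges run from the two-group SD to the three-group pooled SD.

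| | Power at the printed difference | Difference detectable at 80% |
|---|---|---|
| Brain, two tests | 67–69% | 45–46% |
| Brain, three tests | 60–63% | 48–49% |
| Lung, two tests | 57–61% | 28–30% |
| Lung, three tests | 49–54% | 30–32% |

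If all 12 recruited per group complete, t-based brain power is 77–78% (two tests) or 71–73% (three).

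**Step 5: one ordered contrast.** Scoring the genotypes 0, 1, 2 by number of L alleles and centring gives weights −1, 0, +1 when groups are equal. The test is (mean LL − mean HH) ÷ (pooled SD × √(2/n)) on 3n − 3 df. It is one test per organ, so 5% holds per organ without adjustment. Its power and detectable differences are the pooled-SD figures above: brain 79% at a 40% difference, 80% at 40.4%; lung 73% at 23%, 80% at 25.0%.

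**The case against.** The strongest reply is that Section 12 states a difference from the HH mean for a single comparison and claims neither family-wise control nor joint power. No test is named, and the choice among trend, overall and pairwise tests, with any multiplicity rule, may sit in an analysis plan that is not shown. This stands: the absence of a multiplicity procedure is not in itself the fault. What the protocol does fix is the sample-size statement, which carries a one-comparison figure over to several contrasts.

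Four stronger readings are tempting, and the protocol does not support them.
- A reader might infer that either the 5% or the 80% must fail. That follows only for separate pairwise tests; one ordered contrast keeps 5% and 79% power in brain.
- A reader might treat brain and lung as one family, with a false-positive chance of 16–23% over four to six tests. Nothing requires this: the Precis puts brain under primary and lung under secondary outcomes.
- A reader might blame the whole lung shortfall on multiplicity. Part of it is the normal approximation: one unadjusted t-based test already has only 70–73% power.
- A reader might say that the printed figures prove a two-group formula. In brain, the three-group pooled contrast (40.4%) is as close as any. What the figures show is a single comparison, not which formula was used.

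The practical harm is also limited. If all 12 per group complete, Bonferroni brain power by the normal approximation is 82% for two tests and 77% for three. The Phase 2 rule has no p-value attached, and its nine subjects lie within the planned 11.

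**Conclusion.** The point holds in a limited form. The 40% and 23% are one-comparison figures at unadjusted 0.05, and neither allows for the two or three genotype contrasts the text refers to. For one comparison the brain figure is approximately right (78–82% power). The lung figure needs restating whatever is decided about multiplicity, because a two-sided t-based test has 70–73% power at 23% with six per group.

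Unadjusted separate tests carry a 9–12% chance of a false difference per organ. Bonferroni within an organ leaves 60–69% power in brain and 49–61% in lung. These results assume two-sided tests, equal SDs across genotypes and, as the protocol itself assumes, that the SD-to-mean ratio of the earlier tracers carries over to ER176.

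**What to change.** In Section 12:
- Make the genotype test in each organ one two-sided 1-df contrast on number of L alleles (0, 1, 2) at alpha 0.05, with the SD pooled over the three groups. The stated co-dominance supports this ordering.
- State the detectable HH–LL difference as about 40% of the HH mean in brain (10 per group) and about 25%, not 23%, in lung (six per group).
- Report the pairwise differences, including HH–HL, as estimates with confidence intervals.

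If separate HH-versus-other tests are kept as a family, restate the detectable differences instead: about 45–46% (two tests) or 48–49% (three tests) in brain, and up to about 30% or 32% in lung.

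The cost is wording only, with no added subjects or scans. The downside is that, with equal groups, the contrast is simply HH–LL, so a departure of HL alone is estimated rather than tested. That deserves a sentence in the protocol, since HH against HL is the earlier result cited in the brain paragraph.
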